10.1.9. Source documents

- Source documents provide evidence for the existence of the participant and substantiate the integrity of the data collected. Source documents are filed at the investigator's site.
- Data reported on the eCRF or entered in the eCRF that are transcribed from source documents must be consistent with the source documents or the discrepancies must be explained. The investigator may need to request previous medical records or transfer records, depending on the study. Also, current medical records must be available.
- Definition of what constitutes source data and its origin can be found in monitoring guidelines.
- The investigator must maintain accurate documentation (source data) that supports the information entered in the eCRF.
- The sponsor or designee will perform monitoring to confirm that data entered into the eCRF by authorized site personnel are accurate, complete, and verifiable from source documents; that the safety and rights of participants are being protected; and that the study is being conducted in accordance with the currently approved protocol and any other study agreements, ICH GCP, and all applicable regulatory requirements.

10.1.10. Study and site start and closure

Start of study and first act of recruitment

The start of study and the first act of recruitment are defined as FSFV (first ICF signature date) at a country-level.

Study/Site termination

VH/GSK or designee reserves the right to close the study site or terminate the study at any time for any reason at the sole discretion of VH/GSK. Study sites will be closed upon study completion. A study site is considered closed when all required documents and study supplies have been collected and a study-site closure visit has been performed.

The investigator may initiate study-site closure at any time, provided there is reasonable cause and sufficient notice is given in advance of the intended termination.

Reasons for the early closure of a study site by the sponsor or investigator may include but are not limited to:

For study termination:

- Discontinuation of further study intervention development

For site termination:

- Failure of the investigator to comply with the protocol, the requirements of the IRB/IEC or local health authorities, the sponsor's procedures, or GCP guidelines
- Inadequate or no recruitment (evaluated after a reasonable amount of time) of participants by the investigator
- Total number of participants included earlier than expected

If the study is prematurely terminated or temporarily suspended, the sponsor shall promptly inform the investigators, the IECs/IRBs, the regulatory authorities, and any contract research organization(s) used in the study of the reason for termination or temporary suspension, as specified by the applicable regulatory requirements. The investigator shall promptly inform the participant and should assure appropriate participant therapy and/or follow-up.

10.1.11. Publication policy

The results of this study may be published in peer reviewed scientific literature and/or presented at scientific meetings. The sponsor will comply with the requirements for publication of study results in accordance with standard editorial and ethical practice and as per the sponsor's internal policy. Authorship will be determined by mutual agreement and in line with ICMJE authorship requirements.

10.2. Appendix 2: Clinical laboratory tests

The clinical safety laboratory tests detailed in [Table 9](#) will be performed by the central laboratory. Protocol-specific requirements for inclusion or exclusion of participants are detailed in [Section 5](#) of the protocol. Additional tests may be performed at any time during the study as determined necessary by the investigator or required by local regulations. Investigators must document their review of each laboratory safety report.

Local safety laboratory results are only required if the investigator anticipates that the central laboratory results will not be available in time to support the administration of study intervention and/or to properly evaluate the participant.

If a local safety sample is required, it is important that the sample for central analysis is obtained at the same time. If the central laboratory results significantly differ from the local results, then the local results will be transcribed into the eCRF (units, normal range and certification will need to be reported). If the central results corroborate the local results, then the local results will be retained in the source documents and not transcribed into the eCRF. Local genotypic/phenotypic nor HIV-1 RNA results should be entered into the eCRF.

Table 9 Protocol-required Safety Laboratory Tests

Laboratory Assessments	Parameters	
Coagulation	Prothrombin time (PT) Partial thromboplastin time (PTT) International normalized ratio (INR)	
Hematology	Hemoglobin Hematocrit Platelet count Red blood cell (RBC) count	Mean corpuscular volume (MCV) Mean corpuscular hemoglobin (MCH) Percent reticulocytes
	RBC indices	Neutrophils Lymphocytes Monocytes Eosinophils Basophils
	White blood cell (WBC) count with differential	
Clinical Chemistry¹	Amylase Lipase Creatine phosphokinase (CPK) ² Glucose Calcium Sodium Potassium Blood urea nitrogen (BUN) Creatinine ³	

Laboratory Assessments	Parameters
	Total protein Total and direct bilirubin Alkaline phosphatase ⁴ Aspartate aminotransferase (AST or SGOT) Alanine aminotransferase (ALT or SGPT) Total Bile Acid (TBA)
Lipid Panel (fasting)	Triglycerides Total cholesterol Low-density lipoprotein (LDL) cholesterol High-density lipoprotein (HDL) cholesterol
Routine Urinalysis	Specific gravity Dipstick (pH, glucose, protein, blood, ketones, bilirubin, nitrite, leukocyte esterase) Microscopic examination (if blood or protein is abnormal) to include epithelial cells, RBCs, WBCs, casts, crystals and a culture (if positive, specify pathogen).
Other Tests	
 Highly sensitive (serum or urine) human chorionic gonadotropin (hCG) pregnancy test participants female at birth Follicle-stimulating hormone, if needed to demonstrate that a female is of nonchildbearing potential (See Section 10.4) Serum or urine alcohol, cotinine, and drug screen (to include at minimum: amphetamines, barbiturates, cocaine, opiates, cannabinoids and benzodiazepines) Serology [(HIV antibody 4th generation test, hepatitis B surface antigen [HBsAg], Hepatitis B Core antibody (anti-HBc), Hepatitis B surface antibody (anti-HBs) and if indicated hepatitis B DNA (by PCR), and hepatitis C virus antibody)], with reflex to HCV RNA (by PCR) if positive)

1. Details of liver chemistry stopping criteria and required actions and follow-up assessments after liver stopping or monitoring event are given in Section 10.6. All events of ALT $\geq 3 \times$ upper limit of normal (ULN) and total bilirubin $\geq 2 \times$ ULN ($>35\%$ direct bilirubin) or ALT $\geq 3 \times$ ULN and international normalized ratio (INR) >1.5 , if INR measured, which may indicate severe liver injury (possible Hy's law), must be reported to VH/GSK in an expedited manner (excluding studies of hepatic impairment or cirrhosis). Laboratory analytes to be tested will include the routine liver panel and additional analytes [such as lactate dehydrogenase (LDH), gamma-glutamyl transferase (GGT), glutamate dehydrogenase (GLDH) and serum albumin].
2. Recommend repeat testing if CPK is elevated to ensure the result is transient or due to exercise. A history regarding use of drugs known to cause increase of CPK (such as statins), physical activity or exercise preceding the CPK evaluation should be obtained.
3. Estimated serum creatinine clearance (using the Chronic Kidney Disease Epidemiology Collaboration CKD-EPI method [Delgado, 2021].
4. at screening for eligibility determination ([creatinine clearance (eGFR) of < 50 mL/min/1.73 m²].
5. If alkaline phosphatase is elevated, consider fractionating.

10.3. Appendix 3: AEs and SAEs: Definitions and procedures for recording, evaluating, follow-up, and reporting

10.3.1. Definition of AE

AE definition

• An AE is any untoward medical occurrence in a clinical study participant, temporally associated with the use of a study intervention, whether or not considered related to the study intervention.• NOTE: An AE can therefore be any unfavorable and unintended sign (including an abnormal laboratory finding), symptom, or disease (new or exacerbated) temporally associated with the use of a study intervention.

Events Meeting the AE Definition

• Any abnormal laboratory test results (hematology, clinical chemistry, or urinalysis) or other safety assessments (e.g., ECG, radiological scans, vital signs measurements), including those that worsen from baseline, considered clinically significant in the medical and scientific judgment of the investigator (i.e., not related to progression of underlying disease).• Exacerbation of a chronic or intermittent pre-existing condition including either an increase in frequency and/or intensity of the condition.• New condition detected or diagnosed after study intervention administration even though it may have been present before the start of the study.• Signs, symptoms, or the clinical sequelae of a suspected intervention- intervention interaction.• Signs, symptoms, or the clinical sequelae of a suspected overdose of either study intervention or a concomitant medication. Overdose per se will not be reported as an AE/SAE unless it is an intentional overdose taken with possible suicidal/self-harming intent. Such overdoses should be reported regardless of sequelae.• Events that occur as a result of protocol-mandated procedures (i.e., invasive procedures, modification of participant's previous therapeutic regimen).• "Lack of efficacy" or "failure of expected pharmacological action" per se will not be reported as an AE or SAE. Such instances will be captured in the efficacy assessments. However, the signs, symptoms, and/or clinical sequelae resulting from lack of efficacy will be reported as AE or SAE if they fulfill the definition of an AE or SAE.
Events NOT Meeting the AE Definition

- Any clinically significant abnormal laboratory findings or other abnormal safety assessments that are associated with the underlying disease, unless judged by the investigator to be more severe than expected for the participant's condition.
- The disease/disorder being studied or expected progression, signs, or symptoms of the disease/disorder being studied, unless more severe than expected for the participant's condition.
- Medical or surgical procedure (e.g., endoscopy, appendectomy): the condition that leads to the procedure is the AE.
- Situations in which an untoward medical occurrence did not occur (social and/or convenience admission to a hospital, admission for routine examination.).
- Anticipated day-to-day fluctuations of pre-existing disease(s) or condition(s) present or detected at the start of the study that do not worsen. Pre-existing diseases will be recorded in the medical history section of the eCRF.
- Hospitalization for elective treatment of a pre-existing condition (known or diagnosed before signing the informed consent) that did not worsen from baseline.
- DRE, typically associated with the disease under study. These events will be recorded in the participant's eCRF and will be monitored by SRT on a routine basis. However, if 1 or both of the following conditions apply, then the event should be reported promptly to VH/GSK as an SAE (see Section [8.4.9](#)):
 - The event is, in the investigator's opinion, of greater intensity, frequency, or duration than expected for the individual participant, or
 - The investigator considers that there is a reasonable possibility that the event was related to the administration of the study intervention

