8.3.7. Study Pausing Rules

Participant safety will be continuously monitored by the VH medical monitor and the GSK safety lead. Pertinent findings and conclusions are shared with the product's SRT for review of the overall benefit-risk profile of the product. The sponsor's governance

group, the ViiV Safety and Labelling Committee (VSLC) will review data and the team's recommendation when any pausing/stopping rules are met. The VSLC will govern whether enrollment may be resumed/modified, a given treatment arm will be stopped, or the study stopped.

The following study pausing criteria would be applied per compound:

- Any SAE, regardless of its severity, that is considered to be clinically significant and reasonably attributable to dosing with VH4004280 or VH4011499, in the opinion of the investigator or the Sponsor.
- Any Grade 3 or higher rash or Grade 2 rash with evidence of systemic involvement that the investigator considers reasonably attributable to VH4004280 or VH4011499.
- Any Grade 4 AE or laboratory abnormalities (with the exception of an asymptomatic Grade 4 lipid abnormalities or CPK increase) that the investigator considers reasonably attributable to VH4004280 or VH4011499.
- Any participant meeting liver stopping criteria that the investigator considers reasonably attributable to VH4004280 or VH4011499.
- Any participant meeting QTc stopping criteria that the investigator considers reasonably attributable to VH4004280 or VH4011499.

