8.4.7. Disease-related events and/or disease-related outcomes not qualifying as AEs or SAEs

The events or outcomes listed in the CDC Classification System for HIV-1 Infections (Section 10.8) will be recorded on the HIV-Associated Conditions eCRF page if they occur. However, these individual events or outcomes, as well as any sign, symptom, diagnosis, illness, and/or clinical laboratory abnormality that can be linked to any of these events or outcomes are not reported to VH/GSK as AEs and SAEs even though such event or outcome may meet the definition of an AE or SAE, **unless the following conditions apply:**

- The investigator determines that the event or outcome qualifies as an SAE under part 'f' of the SAE definition [Section 10.3.2], or
- The event or outcome is in the investigator's opinion of greater intensity, frequency or duration than expected for the individual participant, or
- The investigator considers that there is a reasonable possibility that the event was related to study intervention.
- Death occurring for any reason during a study, including death due to a disease-related event, will always be reported promptly, or
- Lymphomas and invasive cervical carcinomas are excluded from this exemption; they must be reported as SAEs even if they are considered to be HIV-related.

If any of the above conditions are met then record the Disease Related Event on the SAE page rather than the HIV Associated Conditions eCRF.

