10.3.2. Definition of SAE

An SAE is defined as any untoward medical occurrence that, at any dose, meets one or more of the criteria listed:

a. Results in death

b. Is life threatening

The term 'life-threatening' in the definition of 'serious' refers to an event in which the participant was at risk of death at the time of the event. It does not refer to an event, which hypothetically might have caused death, if it were more severe.

c. Requires inpatient hospitalization or prolongation of existing hospitalization

- In general, hospitalization signifies that the participant has been admitted (usually involving at least an overnight stay) at the hospital or emergency ward for observation and/or treatment that would not have been appropriate in the physician's office or outpatient setting. Complications that occur during hospitalization are AE. If a complication prolongs hospitalization or fulfills any

other serious criteria, the event is serious. When in doubt as to whether “hospitalization” occurred or was necessary, the AE should be considered serious.

 • Hospitalization for elective treatment of a pre-existing condition that did not worsen from baseline is not considered an AE.

 d. Results in persistent or significant disability/incapacity 
 • The term disability means a substantial disruption of a person’s ability to conduct normal life functions. • This definition is not intended to include experiences of relatively minor medical significance such as uncomplicated headache, nausea, vomiting, diarrhea, influenza, and accidental trauma (e.g., sprained ankle) that may interfere with or prevent everyday life functions but do not constitute a substantial disruption.

 e. Is a congenital anomaly/birth defect in the offspring of a study participant

 f. Abnormal pregnancy outcomes (e.g., spontaneous abortion, fetal death, stillbirth, congenital anomalies, ectopic pregnancy)

 g. Is a suspected transmission of any infectious agent via an authorized medicinal product

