10.3.6.2. Assessment of intensity

The investigator will make an assessment of intensity for each AE and SAE reported during the study and assign it to one of the following categories according to the DAIDS toxicity scales (refer to Section 10.7).

Where a DAIDS toxicity scale is not available for a particular event or parameter, then the investigator will instead make an assessment of intensity using one of the severity categories described in the functional DAIDS table shown in Section 10.7.

Note: An event is defined as ‘serious’ when it meets at least one of the pre-defined outcomes as described in the definition of an SAE.

Note: Grade 4 DAIDS toxicity grades for laboratory parameters that are asymptomatic would not necessarily be considered SAEs, a clinical correlation would be necessary.

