4.3.2.1. Adverse Events analyses

AEs will be coded to the preferred term (PT) level using the Medical Dictionary for Regulatory Affairs (MedDRA) using the latest version at time of database release. AEs will be graded by the investigator according to the Division of AIDS (DAIDS) Criteria Version 2.1.

The number and percentage of participants reporting AEs during the monotherapy period will be summarised using the following categories and subcategories:

- AEs
 - By System Organ Class and Maximum Grade
- AEs leading to permanent discontinuation of study treatment
- Drug-related AEs
 - Overall
 - By Maximum Grade
- Drug-related Non-serious AEs
- Common ($\geq 5\%$) non-Serious AEs
- SAEs by System Organ Class and Maximum Grade
- Drug-related SAEs

The Common ($\geq 5\%$) non-Serious AEs display will also include the number of events of an AE.

Selected displays from the above list will be repeated for AEs with onset during the Follow-Up period and during either the monotherapy or the Follow-Up period. AEs with onset in the monotherapy period which continue in the Follow-Up period will only be included in AE summaries for the monotherapy period. See OPS for the exact AE tables to be repeated for Follow-Up and monotherapy + Follow-Up.

A listing of all AEs and a listing of reasons for considering as SAE will be provided.

All planned AE displays are provided in the OPS document.

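### Protocol 10.3.1 and 8.4.7 send disease-related events to SAE reporting when they are related or worse than expected, without requiring seriousness, which contradicts the protocol's own SAE definition

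*Protocol*

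**What the plan says.** Protocol 10.3.1 lists disease-related events among those that do not meet the AE definition, then makes an exception: "if 1 or both of the following conditions apply, then the event should be reported promptly to VH/GSK as an SAE". The first condition is that the event is, in the investigator's opinion, "of greater intensity, frequency, or duration than expected for the individual participant, or" and the second reads: "The investigator considers that there is a reasonable possibility that the event was related to the administration of the study intervention".

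Protocol 8.4.7 exempts CDC-listed HIV conditions, and any sign, symptom, diagnosis or laboratory abnormality linked to them, from AE and SAE reporting unless one of several conditions applies. The same two triggers are among these conditions. If any is met, the site is told to "then record the Disease Related Event on the SAE page rather than the HIV Associated Conditions eCRF".

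The general definitions differ. Under 10.3.2, "An SAE is defined as any untoward medical occurrence that, at any dose, meets one or more of the criteria listed", with criteria lettered a to h. Under 10.3.6.2 an event is serious "when it meets at least one of the pre-defined outcomes as described in the definition of an SAE".

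Two parts of the plan use SAE status downstream. The first pausing criterion in Protocol 8.3.7 covers "Any SAE, regardless of its severity, that is considered to be clinically significant and reasonably attributable to dosing" with either compound. SAP 4.3.2.1 plans "SAEs by System Organ Class and Maximum Grade", a table of drug-related SAEs, a separate table of drug-related non-serious AEs, and a listing of why each SAE was considered serious. Protocol 6.4 also lets the sponsor's global safety staff unblind any participant who has an SAE.

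**The concern.** Relatedness is a causality judgement. A worse-than-expected course is a judgement about severity or time course. Neither is a seriousness outcome, so the disease-related-event wording applies a different test from the rest of the protocol. Two investigators with the same non-serious event could class it differently, depending on which section they follow.

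What is at stake is the reading of the safety tables in a trial with six participants per active arm and one or two per placebo group in each part. A false SAE, especially one labelled drug-related, would stand out at that size. It would also give sponsor safety staff grounds to unblind a participant whose event does not meet the protocol's own seriousness definition.

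**Working it through.** The plan states no figure on this point, so the check is mainly a comparison of the text.

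**Step 1. Do the triggers match the SAE criteria?** Criteria a to h in 10.3.2 cover death, threat to life, hospitalization, disability, congenital anomaly, abnormal pregnancy outcome, transmission of an infectious agent, and other situations (possible Hy's Law, or medical judgement about significant events). Relatedness is not on the list, and neither is a worse-than-expected course. Criterion h lets judgement make some disease-related events serious, but it does not make all related or worse-than-expected events serious.

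**Step 2. Is 10.3.1 consistent with itself?** Its bullets on the disease under study and on disease-associated laboratory findings lift the AE exclusion when the finding is more severe than expected. That makes the finding an AE. The disease-related-event bullet sends the same class of event to SAE reporting. Section 10.3.6.2 adds that even an asymptomatic Grade 4 laboratory value is not necessarily an SAE, which fits poorly with automatic SAE reporting of a mild related sign.

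**Step 3. Does 8.4.7 resolve it?** No. Its lead sentence exempts events from both AE and SAE reporting, so it covers non-serious events. Once the exemption lifts, the only page it names is the SAE page.

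**Step 4. Where does each kind of event go if the text is followed literally?**

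| Disease-related event | Reported as SAE under 10.3.1 | Serious under 10.3.2 | Can reach the first pausing criterion |
|---|---|---|---|
| Worse than expected, unrelated, non-serious | Yes | No | No: not attributable |
| Related, non-serious | Yes | No | Only if also judged clinically significant |
| Meets a criterion in 10.3.2 | Yes, if either trigger is met | Yes | If attributable and clinically significant |

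The first two rows are the misclassified ones.

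**Step 5. What happens in the tables?** The SAP does not say whether the seriousness flag comes from the page used or from a criterion met, and it gives no rule for disease-related events. If the flag follows the SAE page, both misclassified rows enter the SAE table. The second row also enters the drug-related SAE table and drops out of the drug-related non-serious AE table. Neither row has a valid reason to show in the SAE-reasons listing.

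**Step 6. How large is one event?** Inputs: 6 per active arm and 2 placebo participants in each of Parts 1a and 1b (Protocol 4.1). Exact (Clopper-Pearson) 95% limits:
- 0/6: lower limit 0; upper limit 1 − 0.025^(1/6) = 0.459.
- 1/6 (16.7%): lower limit 1 − 0.975^(1/6) = 0.004; upper limit 0.641, the p that solves (1 − p)^6 + 6p(1 − p)^5 = 0.025.
- Placebo: 0/2 = 0% becomes 1/2 = 50%.

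These figures show the effect of any single event in groups this small. They say nothing about how often one would occur.

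**The case against.** The strongest defence is that this is cautious over-reporting with little practical reach. Much of that stands.

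- **Pausing rule.** A reader might infer that every such event triggers a study pause, because the first criterion applies regardless of severity. The documents do not support that. Severity means grade, and the criterion also requires clinical significance and attributability. The worse-than-expected condition alone cannot meet it.
- **AE route.** A reader might also infer that these events have no route to the AE page. That is too strong: 10.3.1 gives an AE route for disease signs more severe than expected, and lifting the 8.4.7 exemption can be read as restoring both routes. The fault is that the text points in two directions.
- **Tables.** Counting as an SAE is likely but not certain. The seriousness derivation is not given, and the SAP defers display details to its output specification. The SAE-reasons listing could expose an event with no valid reason.
- **Rarity.** Entry requires a CD4 count of at least 200, follow-up ends at Day 39, and exclusion 3 bars active Stage 3 disease except cutaneous Kaposi's sarcoma not needing systemic therapy. Worsening Kaposi's sarcoma might qualify as serious anyway, since criterion h gives invasive or malignant cancers as examples. Linked signs, symptoms and laboratory abnormalities remain, but the set is small.
- **Endpoints.** SAE incidence is not a named endpoint, and under SAP 4.7 interim safety outputs are pooled across arms within a study part.

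What the defence does not answer is the contradiction. Caution calls for prompt notification. It does not call for labelling a non-serious event an SAE against the protocol's own definition.

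**Conclusion.** The point holds as an internal contradiction in event classification with a limited reach. Protocol 10.3.1 and the last sentence of 8.4.7 conflict with 10.3.2, with 10.3.6.2, and with other bullets in 10.3.1.

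A non-serious disease-related event is liable to be tabulated as an SAE and, if related, as a drug-related SAE. This assumes that sites follow the literal wording and that the seriousness flag follows the SAE page. The unblinding permission in 6.4 would then extend to such an event. The primary efficacy analysis is not affected.

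One event would change an arm's SAE incidence as shown in Step 6. The chance of such an event cannot be derived from the documents, and any probability offered would only restate an assumed rate.

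**What to change.** Reconcile the passages so that seriousness is decided in one place:

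- **Protocol 10.3.1, disease-related-event bullet:** an event meeting either condition is notified promptly to the sponsor and recorded as an AE. It is classed as an SAE only if it meets a criterion in 10.3.2.
- **Protocol 8.4.7, last sentence:** name the AE page, and the SAE page when 10.3.2 is met. Keep the explicit rules for deaths, lymphomas and invasive cervical carcinomas.
- **SAP 4.3.2.1:** state that SAE tables and the SAE-reasons listing use events meeting 10.3.2 or one of those explicit rules.
- **Protocol 8.3.7:** leave the pausing criteria unchanged.

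Two nearby references should be corrected in the same edit. The 10.3.1 bullet cites 8.4.9, which is the participant card. Section 8.4.7 cites part f of the SAE definition, which in 10.3.2 is abnormal pregnancy outcomes. Correcting these alone would not cure the point above.

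The cost is two sentences of protocol wording, one SAP statement and matching eCRF completion guidance. Moving non-serious events off the SAE page would otherwise lose the 24-hour SAE route, so the prompt-notification wording should be kept. With it, the sponsor still hears of these events promptly.
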